6.1 Definition of adverse events

An adverse event is the development of an undesirable medical condition or the deterioration of a pre-existing medical condition following or during exposure to a pharmaceutical product, whether or not considered causally related to the product. An undesirable medical condition can be symptoms (e.g., nausea, chest pain), signs (e.g., tachycardia, enlarged liver) or the abnormal results of an investigation (e.g., laboratory findings, electrocardiogram). In clinical studies, an AE can include an undesirable medical condition occurring at any time, including run-in or washout periods, even if no study treatment has been administered.

The term AE is used to include both serious and non-serious AEs.

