6.3.5 Adverse events based on signs and symptoms

All AEs spontaneously reported by the patient or care provider or reported in response to the open question from the study personnel: 'Have you had any health problems since the previous visit/you were last asked?', or revealed by observation will be collected and recorded in the eCRF. The question will be put to each patient (or parent/legal guardian) in local language from Visit 2 to the last follow-up telephone contact. When collecting AEs, the recording of diagnoses is preferred (when possible) to recording a list of signs and symptoms. However, if a diagnosis is known and there are other signs or symptoms that are not generally part of the diagnosis, the diagnosis and each sign or symptom will be recorded separately.

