6.3.6 Adverse events based on examinations and tests

The results from protocol mandated laboratory tests, vital signs and other safety assessments will be summarized in the CSR. Deterioration as compared to baseline in these parameters will therefore only be reported as AEs if they fulfil any of the SAE criteria or are the reason for discontinuation of treatment with the study drug.

If deterioration in a laboratory value, vital sign or other safety assessment is associated with clinical signs and symptoms, the sign or symptom will be reported as an AE and the associated laboratory result or other finding will be considered as additional information. In the absence of clinical signs and symptoms, clinically relevant deteriorations in non-mandated parameters should be reported as AE(s).

Any new or aggravated clinically relevant abnormal medical finding at a physical examination as compared with the baseline assessment will be reported as an AE.

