6.7 Management of study drug related toxicities

If a patient experiences a CTCAE grade 3 and/or unacceptable toxicity not attributable to the disease or disease-related processes under investigation, dosing will be interrupted and supportive therapy administered as required in accordance with local practice/guidelines.

If a toxicity resolves or reverts to ≤CTCAE grade 2 within 3 weeks of onset, treatment with study drug may be restarted at the same dose (80 mg) or a lower dose (40 mg) using the rules below for dose modifications (Table 3) and with discussion and agreement with the AstraZeneca Study Team Physician as needed. There will be no individual modifications to dosing schedule in response to toxicity, only potential dose reduction or dose interruption.

If the toxicity does not resolve to ≤CTCAE grade 2 after 3 weeks, then the patient should be withdrawn from the study and observed until resolution of the toxicity.

Table 3. OSIMERTINIB dose adjustment information for adverse reactions

Target		
organ	Adverse reaction ^a	Dose modification
Pulmonary	ILD/Pneumonitis	Permanently discontinue OSIMERTINIB
Cardiac	QTc interval greater than 500 msec on at least 2 separate ECGs	Withhold OSIMERTINIB until QTc interval is less than 481 msec or recovery to baseline if baseline QTc is greater than or equal to 481 msec, then restart at a reduced dose (40 mg)
	QTc interval prolongation with signs/symptoms of serious arrhythmia	Permanently discontinue OSIMERTINIB
Other	Grade 3 or higher adverse reaction	Withhold OSIMERTINIB for up to 3 weeks
	If Grade 3 or higher adverse reaction improves to Grade 0-2 after withholding of OSIMERTINIB for up to 3 weeks	OSIMERTINIB may be restarted at the same dose (80 mg) or a lower dose (40 mg)
	Grade 3 or higher adverse reaction that does not improve to Grade 0-2 after withholding for up to 3 weeks	Permanently discontinue OSIMERTINIB

^a Note: The intensity of clinical adverse events graded by the National Cancer Institute (NCI) Common Terminology Criteria for Adverse Events (CTCAE) version 4.0.

ECGs: Electrocardiograms; QTc: QT interval corrected for heart rate

On resolution of toxicity within 3 weeks:

• If an AE subsequently requires dose interruption, study drug may restart at the same dose or the reduced dose, on resolution/improvement of the AE at the discretion of the Investigator.

ILD/Pneumonitis-like toxicity

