8.3 Description of outcome variables in relation to objectives

Analysis will be conducted to evaluate the following as available in the CRF:

- Baseline characteristics: demographics, relevant medical history, disease characteristics, cancer treatment history.
- Exposure to the study drug
- Adverse events SAEs, AEs leading to dose modification or discontinuation, and AEs of special interest (for example interstitial lung disease/pneumonitis-like events; QTc prolongation events)
- Death due to AE, or unknown cause (except death due to disease progression).

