## 8.7 Safety Analysis

### 8.7.1 Adverse Events

All adverse events (AEs) will be coded by System Organ Class (SOC) and Preferred Term (PT) according to the Medical Dictionary for Regulatory Activities (MedDRA) Version 23.0. The intensity of adverse events is graded by the National Cancer Institute (NCI) Common Terminology Criteria for Adverse Events (CTCAE) version 4.0 or higher.

*Treatment-emergent adverse events are adverse events with onset during the treatment phase or that are a consequence of a pre-existing condition that has worsened since baseline. All reported adverse events will be*

*included in the analysis. For each adverse event, the percentage of subjects who experience at least 1 occurrence of the given event will be summarized.*

*Any AE occurring before treatment with osimertinib will be included in the data listings but will not be included in the summary tables of AEs. Any AE occurring within 28 days of discontinuation of investigational product (i.e., the last dose of osimertinib) will be included in the AE summaries.*

*Any events in this period that occur after a patient has received further therapy for cancer (following discontinuation of osimertinib) will be flagged in the data listings.*

*Adverse events of special interest (for example interstitial lung disease/pneumonitis-like events; QTc prolongation events) will be summarized separately.*

*Summaries, listings, datasets, or subject narratives may be provided, as appropriate, for those subjects who die, who discontinue treatment due to an adverse event, or who experience a severe or a serious adverse event.*

An overall summary will be provided in terms of count and percentages for:

- AEs
- TEAEs
- Grade 3 and above TEAEs
- Grade 3 and above related TEAEs
- Treatment-related TEAEs
- Treatment-related serious TEAEs
- TEAEs leading to dose change/ interruption/ discontinuation
- Treatment related TEAEs leading to dose change/ interruption/ discontinuation
- Serious TEAEs
- Fatal TEAEs
- Related Fatal TEAEs

Summaries in terms of count and percentages by SOC and PT will be provided for the following:

- TEAEs
- Treatment-Emergent SAEs
- Grade 3 and above TEAEs
- Treatment-related TEAEs
- Grade 3 and above treatment-related TEAEs
- TEAEs leading to dose change/ interruption/ discontinuation
- Adverse Events of special interest

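### Protocol 6.3.6 can file symptomatic, non-serious QTc prolongation under its symptom alone, so the QTc row of the special-interest AE table can undercount and disagree with the ECG table

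*Protocol*

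**What the plan says.** Protocol 6.3.6 has two rules for scheduled safety tests. Its first paragraph says that worsening from baseline will "only be reported as AEs if they fulfil any of the SAE criteria or are the reason for discontinuation of treatment with the study drug". Its second paragraph covers worsening that comes with symptoms: "the sign or symptom will be reported as an AE and the associated laboratory result or other finding will be considered as additional information". It does not say whether the two exceptions of the first paragraph carry over. The 12-lead ECG is scheduled at screening, on Day 1 of each cycle and at end of treatment (Table 1), so QTc prolongation falls under these rules.

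Two other sections lean the other way. Under 6.3.5, "the recording of diagnoses is preferred (when possible) to recording a list of signs and symptoms", and symptoms that do not belong to the diagnosis are entered separately. Section 6.1 counts abnormal test results among adverse events and gives the ECG as an example.

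Adverse events of special interest (AESI) are part of the primary outcome (Protocol section 2). QTc prolongation is one of the two examples of AESI in Protocol 8.3 and 8.5.1. SAP 8.7.1 states: "Adverse events of special interest (for example interstitial lung disease/pneumonitis-like events; QTc prolongation events) will be summarized separately". It tabulates them by system organ class and preferred term, and Protocol 8.5.1 has coding start from the investigator's verbatim term. SAP 8.7.4 separately tabulates maximum QTc and maximum increase by category in each cycle, and the frequency of ECG abnormalities.

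**The concern.** The recording rule and the AESI table do not fit together. The table counts coded terms. For a symptomatic ECG finding, the rule says that the symptom becomes the term. An investigator who follows 6.3.6 literally enters palpitations; one who follows 6.3.5 or 6.1 enters QTc prolongation. The same event then lands in different rows depending on which paragraph the site applied, and any error in the QTc row is downward. In a trial of about 60 patients whose only objective is safety, the difference between one QTc event and none is what a reader will take from that row.

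**Working it through.** **Step 1. Which events are exposed.** Applying both paragraphs of 6.3.6 to QTc prolongation on a scheduled ECG:

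| | Serious, or ends treatment | Neither |
|---|---|---|
| With symptoms | Finding is an AE under paragraph 1; paragraph 2 does not confirm it | Symptom is the AE, finding is not: **the gap** |
| Without symptoms | Finding is an AE under paragraph 1 | Not an AE; appears only in the ECG tables |

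**Step 2. Can the gap cell occur?** Yes. Under Protocol 6.7, QTcF above 500 msec leads to interruption and then a restart after recovery. Permanent withdrawal follows only if recovery fails within the stated time. A symptomatic, non-serious episode can therefore pass without meeting either exception.

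**Step 3. Can the AE record identify such a case later?** Not from the listed items. Protocol 6.3.3 lists, for every AE, the verbatim term, dates, intensity, seriousness, causality, action taken, withdrawal and outcome. There is no field linking the AE to an ECG finding, and a description of the event is listed only for serious events. A dose interruption for the episode would also be tabulated under the symptom's preferred term.

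**Step 4. Size.** Inputs: n = 60 and exact two-sided 95% limits from the beta distribution (Protocol 8.2). For x events:

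- lower = Beta quantile(0.025; x, n − x + 1)
- upper = Beta quantile(0.975; x + 1, n − x)

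Check against the plan: x = 3 (5%) gives 1.0 to 13.9, and x = 0 gives 0 to 6.0, both as printed. All nine printed rows reproduce. The 1% and 2% rows correspond to 0.6 and 1.2 patients, so the interval for one patient is not in the table and has to be computed.

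The documents give no QTc event rate, so the counts are assumptions. If exactly one patient has an event of the gap type:

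- recorded as QTc prolongation: 1/60 = 1.7%, 95% CI 0.04 to 8.9
- recorded as its symptom: 0/60 = 0%, upper limit 1 − 0.025^(1/60) = 5.96%, so 0 to 6.0

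If three patients have gap-type events, the row shows 3/60 = 5.0% (1.0 to 13.9) when all are recorded as QTc, 2/60 = 3.3% (0.4 to 11.5) when one is lost, 1/60 = 1.7% (0.04 to 8.9) when two are lost, and 0/60 when all are lost.

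Next, take p as the assumed true rate of gap-type events and f as the assumed share entered only as a symptom. The chance that at least one of them reaches the row is 1 − (1 − p(1 − f))^60:

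| p | f = 0 | f = 25% | f = 50% |
|---|---|---|---|
| 1% | 45% | 36% | 26% |
| 2% | 70% | 60% | 45% |
| 5% | 95% | 90% | 78% |

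At f = 100% it is zero for every p.

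**The case against.** The case against is substantial, and most of it limits the point.

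- **The gravest events are normally captured.** A reader might infer that symptomatic arrhythmia cases are the ones lost. The documents do not support that. Table 3 makes "QTc interval prolongation with signs/symptoms of serious arrhythmia" a ground for permanent discontinuation, and paragraph 1 of 6.3.6 makes a finding that ends treatment, or is serious, an AE. What remains is that paragraph 2 does not say so for symptomatic findings.
- **The QTc data are still reported.** A reader might infer that the report would say no QTc prolongation occurred, or that cases could not be recovered. SAP 8.7.4 shows the QTc categories and abnormality frequencies, and patient-level ECG records exist. Only the AESI row is at risk.
- **6.3.5 is a preference.** It applies where possible, and it conflicts with 6.3.6 only if QTc prolongation is treated as a diagnosis. This is tension, not contradiction. Section 6.1 supports the point independently.
- **Mixed illustrations fail.** It is tempting to show asymptomatic cases staying in the row while a symptomatic one drops out. Asymptomatic, non-serious changes that do not end treatment are not AEs under paragraph 1 either, so they would not be in the row.
- **Cytopenias do not extend the point far.** They are not named as AESI, and laboratory toxicity grades and shift tables are planned.
- **Selection by preferred term is partly inferred.** SAP 8.7.1 gives a display by preferred term and no explicit selection rule. But neither document draws AESI from ECG values, so coded terms are the only route described.

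**Conclusion.** The point holds in a narrow form. Symptomatic, non-serious QTc prolongation managed without permanent discontinuation can be coded to a symptom term only. It is then missing from the QTc AESI row, while SAP 8.7.4 shows the prolonged value. No rule reconciles the two tables. In absolute terms the effect is one or a few patients out of 60, and the intervals overlap heavily. It matters because it can turn one event into none in a component of the primary outcome, and because it can vary by site. The conclusion rests on two readings: that sites follow paragraph 2 of 6.3.6 as written, and that the AESI row is filled from coded terms. The counts are illustrative, since the documents give no QTc event rate and no share recorded as symptoms. The point is worth correcting but does not threaten the trial.

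**What to change.** **Protocol 6.3.6 and the eCRF instructions.** Reword paragraph 2 so that, when a safety finding explains the symptom, the finding or diagnosis is recorded as an AE under its own term. This should apply at least to QTc prolongation, as an AESI. Symptoms that the finding does not explain are entered separately. State that the seriousness and discontinuation exceptions also apply to symptomatic findings.

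**SAP 8.7.1.** State that the QTc AESI row also counts patients with a symptom AE whose concurrent ECG record shows QTc prolongation. The case must be identified from the ECG record (the QTc value analysed in SAP 8.7.4, or the abnormality specified under Protocol 5.1.3), because no AE field carries the link. Fix in advance which QTc category counts and how close in time the ECG must be. Scheduled ECGs during treatment are about one 21-day cycle apart, so some symptoms will have no ECG near them. Add a short listing that reconciles the AESI row with the 8.7.4 table. It will also show the asymptomatic cases that properly appear only in 8.7.4.

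The cost is a small wording change, minor extra programming and possibly a slightly higher reported QTc AESI rate. No new procedures are needed. If data collection has already closed, the SAP part can still be applied alone.

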6.3.7 Disease progression

Disease progression can be considered as a worsening of a patient's condition attributable to the disease for which the investigational product is being studied. It may be an increase in the severity of the disease under study and/or increases in the symptoms of the disease. The development of new, or progression of existing metastasis to the primary cancer under study should be considered as disease progression and not an AE. Events that are unequivocally due to disease progression should not be reported as AEs during the study.

6.3.8 New cancers

The development of a new cancer should be regarded as an AE and will generally meet at least one of the serious criteria. New cancers are those that are not the primary reason for the administration of the study treatment and have been identified after the patient's inclusion in this study. They do not include metastases of the original cancer.

6.5 Overdose

The risks associated with over dosage of osimertinib are considered to be small.

In phase I/II clinical trials a limited number of patients were treated with osimertinib daily doses of up to 240 mg without dose limiting toxicities. In these studies, patients who were treated with osimertinib daily doses of 160 mg and 240 mg experienced an increase in the frequency and severity of a number of typical EGFR TKI-induced AEs (primarily diarrhoea and skin rash) compared to the 80 mg dose. There is limited experience with accidental overdoses in humans. All cases were isolated incidents of patients taking an additional daily dose of osimertinib in error, without any resulting clinical consequences. There is no specific

treatment in the event of osimertinib overdose. In case of suspected overdose, osimertinib should be withheld and symptomatic treatment initiated.

- An overdose with associated AEs is recorded as the AE diagnosis/symptoms on the relevant AE modules in the CRF and on the Overdose CRF module.
- An overdose without associated symptoms is only reported on the Overdose CRF module.

If an overdose on an AstraZeneca study drug occurs in the course of the study, then the Investigator or other site personnel inform appropriate AstraZeneca representatives immediately, or **no later than 24 hours** of when he or she becomes aware of it.

The designated AstraZeneca representative works with the Investigator to ensure that all relevant information is provided to the AstraZeneca Patient Safety data entry site.

For overdoses associated with a SAE, the standard reporting timelines apply, see Section 6.4. For other overdoses, reporting must occur within 30 days.

6.6 Pregnancy

All pregnancies and outcomes of pregnancy occurring during the course of the study and within 6 weeks of the last dose of TAGRISSO should be reported to Astrazeneca.

6.6.1 Maternal exposure

If a patient becomes pregnant during the course of the study, study drug should be discontinued immediately.

Pregnancy itself is not regarded as an adverse event unless there is a suspicion that the investigational product under study may have interfered with the effectiveness of a contraceptive medication. Congenital abnormalities/birth defects and spontaneous miscarriages should be reported and handled as SAEs. Elective abortions without complications should not be handled as AEs. The outcome of all pregnancies (spontaneous miscarriage, elective termination, ectopic pregnancy, normal birth or congenital abnormality) should be followed up and documented even if the subject was discontinued from the study.

If any pregnancy occurs in the course of the study or within 6 weeks of the final dose of the investigational product, then the Investigator or other site personnel informs the appropriate AstraZeneca representatives within 1 day i.e., immediately but no later than 24 hours of when he or she becomes aware of it.

The designated AstraZeneca representative works with the Investigator to ensure that all relevant information is provided to the AstraZeneca Patient Safety data entry site within 1 or 5 calendar days for SAEs (see Section X) and within 30 days for all other pregnancies.

The same timelines apply when outcome information is available.

6.6.2 Paternal exposure

Pregnancy of the subject's partners is not considered to be an adverse event. However, the outcome of all pregnancies (spontaneous miscarriage, elective termination, ectopic pregnancy, normal birth or congenital abnormality) should if possible be followed up and documented.

To capture information about a pregnancy from the partner of a male subject, the male subject's partner consent must be obtained to collect information related to the pregnancy and outcome; the male subject should not be asked to provide this information. A consent form specific to this situation must be used. The outcome of any conception occurring from the date of the first dose until 4 months after dosing ends should be followed up and documented.

6.7 Management of study drug related toxicities

If a patient experiences a CTCAE grade 3 and/or unacceptable toxicity not attributable to the disease or disease-related processes under investigation, dosing will be interrupted and supportive therapy administered as required in accordance with local practice/guidelines.

If a toxicity resolves or reverts to ≤CTCAE grade 2 within 3 weeks of onset, treatment with study drug may be restarted at the same dose (80 mg) or a lower dose (40 mg) using the rules below for dose modifications (Table 3) and with discussion and agreement with the AstraZeneca Study Team Physician as needed. There will be no individual modifications to dosing schedule in response to toxicity, only potential dose reduction or dose interruption.

If the toxicity does not resolve to ≤CTCAE grade 2 after 3 weeks, then the patient should be withdrawn from the study and observed until resolution of the toxicity.

Table 3. OSIMERTINIB dose adjustment information for adverse reactions

Target		
organ	Adverse reaction ^a	Dose modification
Pulmonary	ILD/Pneumonitis	Permanently discontinue OSIMERTINIB
Cardiac	QTc interval greater than 500 msec on at least 2 separate ECGs	Withhold OSIMERTINIB until QTc interval is less than 481 msec or recovery to baseline if baseline QTc is greater than or equal to 481 msec, then restart at a reduced dose (40 mg)
	QTc interval prolongation with signs/symptoms of serious arrhythmia	Permanently discontinue OSIMERTINIB
Other	Grade 3 or higher adverse reaction	Withhold OSIMERTINIB for up to 3 weeks
	If Grade 3 or higher adverse reaction improves to Grade 0-2 after withholding of OSIMERTINIB for up to 3 weeks	OSIMERTINIB may be restarted at the same dose (80 mg) or a lower dose (40 mg)
	Grade 3 or higher adverse reaction that does not improve to Grade 0-2 after withholding for up to 3 weeks	Permanently discontinue OSIMERTINIB

^a Note: The intensity of clinical adverse events graded by the National Cancer Institute (NCI) Common Terminology Criteria for Adverse Events (CTCAE) version 4.0.

ECGs: Electrocardiograms; QTc: QT interval corrected for heart rate

On resolution of toxicity within 3 weeks:

• If an AE subsequently requires dose interruption, study drug may restart at the same dose or the reduced dose, on resolution/improvement of the AE at the discretion of the Investigator.

ILD/Pneumonitis-like toxicity

If new or worsening pulmonary symptoms (e.g., dyspnoea) or radiological abnormality suggestive of interstitial lung disease is observed, an interruption in study treatment dosing is recommended, and the AstraZeneca study team should be informed. It is strongly recommended to perform a full diagnostic workup, to exclude alternative causes such as lymphangitic carcinomatosis, infection, allergy, cardiogenic edema, or pulmonary hemorrhage. The results of the full diagnostic workup (including high-resolution computed tomography, blood and sputum culture, haematological parameters) will be recorded in the CRF by the investigator. In the presence of confirmatory HRCT scans where other causes of respiratory symptoms have been excluded, a diagnosis of interstitial lung disease (ILD) should be considered and study treatment permanently discontinued.

In the absence of a diagnosis of ILD study treatment may be restarted following consultation with the AstraZeneca Study Team Physician.

QTc prolongation

Patients with QTcF prolongation to >500 msec should have study treatment interrupted and regular ECGs performed until resolution to <481 msec or recovery to baseline if baseline QTcF is >481 msec and then restarted at a reduced dose of 40 mg. If the toxicity does not resolve to ≤grade 1 within 21 days the patient will be permanently withdrawn from study treatment.

Keratitis

Patients presenting with signs and symptoms suggestive of keratitis such as acute or worsening: eye inflammation, lacrimation, light sensitivity, blurred vision, eye pain and/or red eye should be referred promptly to an ophthalmology specialist.

Changes in cardiac contractility

In patients with cardiac risk factors and those with conditions that can affect LVEF, cardiac monitoring, including an assessment of LVEF at baseline and during treatment, should be considered. In patients who develop relevant cardiac signs/symptoms during treatment, cardiac monitoring including LVEF assessment should be considered.

Patients experiencing corneal ulceration, Interstitial Lung Disease (ILD) or QTc prolongation with signs/symptoms of serious arrythmia will not be permitted to restart study treatment.

For the details, please refer to the local prescribing information.

7. Study Drug and Other Treatments

Osimertinib is an oral, potent, selective, irreversible inhibitor of both EGFR-TKI sensitising and resistance mutations in NSCLC with a significant selectivity margin over wild-type EGFR. osimertinib will be administered orally as one 80 mg tablet once a day. A cycle of

treatment is defined as 21 days of once daily osimertinib treatment. Dose modification will be done as per locally approved prescribing information with the use of 40 mg tablet strength if required.

The study drug Dosage form and strength

Osimertinib 40 mg Tablets 80 mg Tablets

The tablets can be taken with or without food and should be swallowed whole with water. The tablet should not be crushed, split or chewed.

If the patient is unable to swallow the tablet, it may first be dispersed in 50 mL of non-carbonated water. The tablet should be dropped in the water, without crushing, stirred until dispersed and immediately swallowed. An additional 100mL of water should be added to ensure that no residue remains and then immediately swallowed.

Doses should be taken approximately 24 hours apart at the same time point each day. Doses should not be missed. If a patient misses a scheduled dose, within a window of 12 hours, it is acceptable to take the dose. If it is more than 12 hours after the scheduled dose time, the missed dose must not be taken, and patients must be instructed to take the next dose at the next scheduled time. If a patient vomits after taking their study drug treatment, they must not make up for this dose, but must take the next scheduled dose.

Any change from dosing schedule, dose interruptions, or dose reductions must be recorded in the CRF.

The study drug will be administered according to the prescribing information of the approved label by the investigator.

